9.7 Interim Monitoring of Toxic Death

Toxic death is death predominantly attributable to treatment-related causes. The occurrence

of toxic death at any time will be a primary endpoint for safety monitoring. Any toxic death on study will be reviewed with CTEP and the DMSC prior to continuing enrollment on study. The study will be stopped if there are two toxic deaths on study.

9.8 Analysis of Toxicity

Estimates will be obtained using life-table methods, with an event defined as the first occurrence of a primary toxicity. Time scale used in the time to first occurrence of a key acute and subacute toxicity is time in days since the start of therapy. Patients who have progression or recurrence of disease will be censored in these analyses. The rates of individual toxicities in each course of treatment, the number of patients who require a dose reduction and number of patients who come off protocol therapy due to toxicity will be summarized using standard descriptive statistical methods. To evaluate hematologic toxicity of long term lenalidomide administration adverse event data will be collected using CTCAE version 4 toxicity coding. Grade 3 or greater hematologic toxicities will be recorded per reporting period and compared between 2 lenalidomide doses

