This study is a randomized comparison of response rate among patients with recurrent, refractory or progressive juvenile pilocytic astrocytomas and optic pathway gliomas who are treated with lenalidomide. Lenalidomide will be given either as a low dose (20 mg/m²/dose) or high dose (115 mg/m²/dose) regimen PO for 21 days of each 28 day cycle. Treatment will continue for a maximum of 26 cycles in the absence of disease progression or unacceptable side effects. Response will be evaluated prior to every other cycle for the first 13 cycles and prior to every third cycle for cycles 14-26. Correlation of steady state pharmacokinetic levels with patient outcome will be performed.

EXPERIMENTAL DESIGN SCHEMA

Note: Each cycle is 28 days

PD = Progressive Disease

SD = Stable Disease

PR = Partial Response

CR = Complete Response

1.0**GOALS AND OBJECTIVES (SCIENTIFIC AIMS)****1.1****Primary Objective**

To determine the objective response rate of children with recurrent, refractory or progressive juvenile pilocytic astrocytomas and optic pathway gliomas who are treated with Regimen A low-dose (20 mg/m²/dose) or Regimen B high-dose (115 mg/m²/dose) lenalidomide.

1.2**Secondary Objectives****1.2.1**

To estimate the event-free survival (EFS) (based on standard two-dimensional tumor measurements, determined by each institution) of children with recurrent, refractory or progressive juvenile pilocytic astrocytomas and optic pathway gliomas who are treated with lenalidomide.

1.2.2

To compare response categories and EFS across the 3 MR sequences (T2-weighted, FLAIR, T1-weighted post-contrast).

1.2.3

To correlate steady state pharmacokinetics of lenalidomide (1 sample obtained between Days 5-21) with objective response and EFS.

1.2.4

To evaluate toxicities of long term lenalidomide use.

2.0**BACKGROUND****2.1****Introduction/Rationale for Development**

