- confirmation of negative serum or urine pregnancy test (sensitivity of at least 25 mIU/mL) in female patients of childbearing potential,
- confirmation of the use of 2 forms of effective birth control for female patients of childbearing potential OR confirmation of commitment to complete abstinence, and
- completion and documentation of required lenalidomide education and counseling (all patients)

Dose calculations should be based on actual BSA and adjusted as necessary prior to each cycle. There is no maximum dosing.

Lenalidomide: PO once daily

Days: 1 through 21.

Dose: Regimen A (Low Dose): 20 mg/m²/dose (See [Appendix X](#) for Dosing Tables)
Regimen B (High Dose): 115 mg/m²/dose

Note: The calculated dose should be rounded to within 10% of the prescribed dose for convenience of capsule size. The calculated dose should be rounded in a manner to minimize the daily number of capsules. The dose should be given without food when possible, although this is not mandatory. If a patient vomits a dose within 10 minutes of administration and the capsules are clearly visible, the dose may be repeated. The capsules should be swallowed whole and not opened or chewed.

See [Section 5.0](#) for Dose Modifications based on Toxicities.

The therapy delivery maps (TDMs) for this cycle are on the next two pages. See [Section 4.3.1](#) for the Regimen A (Low Dose: 20 mg/m²/dose) therapy delivery map and [Section 4.3.2](#) for the Regimen B (High Dose: 115 mg/m²/dose) therapy delivery map.

Following completion of the first cycle, the lenalidomide cycle is repeated for up to a total of 26 cycles, as tolerated and in the absence of disease progression (see [Section 10.4](#) for Response Evaluation). If disease progression occurs, the patient will be taken off protocol therapy.

Susbequent lenalidomide cycles should begin on Day 29 or when ANC \geq 1,000/ μ L, platelet count \geq 100,000/ μ L (transfusion independent), whichever occurs later, AND once the following criteria have been met:

- confirmation of negative serum or urine pregnancy test (sensitivity of at least 25 mIU/mL),
- confirmation of the use of 2 effective methods of birth control for female patients of childbearing potential OR confirmation of commitment to complete abstinence,
- completion and documentation of required lenalidomide education and counseling (all patients).

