Disease progression will be based on the results of institutional review. Standard survival methods will be used for analysis of EFS and OS. Analyses include log rank tests and the product-limit (Kaplan-Meier) estimate for estimation of EFS and OS probability. Comparison of EFS between the two dose levels will primarily be exploratory. With 74 patients, we will have only approximately 69% power to detect a 15% increase in long-term EFS (30% to 45%) with 50% patients receiving high dose vs. 50% receiving low dose, based on a one-sided logrank test with 20% Type I error rate.

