9.5 Monitoring for Efficacy

Patients will be randomly assigned to either the low dose or the high dose treatment. Of the 37 patients on each treatment, we will closely monitor the first 20 patients enrolled. For each regimen, the early stopping criterion and the decision regarding ultimate further interest in this agent will be based on the number of objective responses and disease progressions in the first 6 months of treatment. If the early stopping rule is met for one treatment, that particular arm will be closed and the other arm will continue as planned.

A true response rate of 5% and a true early (6-month) progression rate of 40% are considered inadequate, whereas a true response rate of 20% and a true early (6-month) progression rate of 25% would be sufficient for further interest in this agent.

The study will be a 2-stage design, with 20 evaluable patients in the first stage and 17 evaluable patients in the second stage (37 patients total per treatment regimen), with decisions made as follows:

Number of Evaluable Patients Enrolled	Results	Decision
Stage I: 20 evaluable patients	Zero or one responders or 10 or more with early progression	Terminate enrollment with the conclusion the regimen does not demonstrate sufficient disease control
	All other configurations of response or early progression	Continue to the next stage and enroll 17 more patients
Stage II: 17 additional evaluable patients (Total of 37: 20 from Stage I and 17 from Stage II)	Cumulatively 3 or fewer responders or 15 or more with early progression	Conclude the regimen does not demonstrate sufficient disease control
	All other configurations of response or early progression	Conclude the regimen demonstrates sufficient disease control for further investigation

A summary of the operating characteristics of this design are provided below:

Response Probability	Early Progression Probability	Probability of Stopping at First Stage	Probability Accept Regimen
0.05	0.40	0.78	0.05
0.10	0.40	0.51	0.24
0.20	0.30	0.11	0.81
0.15	0.25	0.18	0.73
0.20	0.25	0.08	0.88

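### Section 9.8 censors progression in the life table of first toxicity, so the curve exceeds the share of patients who have the toxicity on treatment, slightly at first and more if carried towards 26 cycles

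*Combined protocol and SAP*

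**What the plan says.** Section 9.8 (Analysis of Toxicity) opens: "Estimates will be obtained using life-table methods, with an event defined as the first occurrence of a primary toxicity". It gives the time scale, in days from the start of therapy, as that of "time to first occurrence of a key acute and subacute toxicity". The next sentence is: "Patients who have progression or recurrence of disease will be censored in these analyses".

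Section 4.3 states: "If disease progression occurs, the patient will be taken off protocol therapy". Section 8.1 lists progressive disease first among the reasons for removal from protocol therapy. The design summary at the front of the protocol allows long exposure: "Treatment will continue for a maximum of 26 cycles in the absence of disease progression or unacceptable side effects".

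Section 9.8 does not define primary toxicity, subacute, a time horizon or the quantity to be estimated. It does not say how death, or withdrawal for reasons other than progression, enters the life table. No cumulative-incidence method is named there or elsewhere in Section 9.

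The same section also plans rates of individual toxicities in each course, counts of patients with dose reductions or removal for toxicity, and a comparison between doses of Grade 3 or higher hematologic toxicity per reporting period.

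**The concern.** A patient who progresses stops lenalidomide and largely leaves the population at risk of a new on-treatment toxicity. Censoring assigns that patient the same future risk as patients still taking the drug. One minus the life-table estimate then describes toxicity if nobody stopped for progression. The share of treated patients who had the toxicity while on treatment is smaller.

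Progression is common under the plan's own assumptions, and treatment can last about two years. The life table is the only cumulative time-to-event toxicity estimate in Section 9.8, and no horizon limits how far the curve is drawn. A family or a later trial team reading the right-hand end as the proportion affected would be given too high a figure.

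**Working it through.** **Is there a stated figure to reproduce?** Section 9.8 gives none. The neighbouring Section 9.6 rule (5 of 18 or 8 of 36 toxic events) can be checked exactly. At a 10% true rate it is met with probability 2.8% at the first look plus 1.4% at the second, 4.2% in all. At 30% it is 66.7% + 23.5%, about 90.3% before rounding of the parts (0.6673 + 0.2353 = 0.9026). Both agree with the stated 4% and 90%. The rule uses simple counts, so the censoring does not touch it.

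**Inputs**

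- Progression, Section 9.5: the plan takes 25% by 6 months as the rate for a regimen worth pursuing and 40% as too high. On the latter it says: "A true response rate of 5% and a true early (6-month) progression rate of 40% are considered inadequate".
- Longest treatment: 26 × 28 = 728 days, 23.9 months.
- Toxicity: no rate is given for primary toxicity. I assume constant hazards and a life-table value of 30% at 12 months, then vary this.

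**Formulas**

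- Hazard from a probability p at time t: h = −ln(1 − p)/t.
- Censored life table, one minus survival: 1 − exp(−hT·t).
- Cumulative incidence with progression competing: hT/(hT + hP) × [1 − exp(−(hT + hP)·t)].

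**Numbers (per month)**

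- hT = −ln(0.70)/12 = 0.0297.
- hP = −ln(0.75)/6 = 0.0479, or −ln(0.60)/6 = 0.0851.
- Life table: 30% at 12 months, 1 − 0.70² = 51% at 24 months.
- With 25% progression: 0.0297/0.0777 = 0.383. Times 0.606 at 12 months gives 0.232; times 0.845 at 24 months gives 0.323.
- With 40% progression: 0.0297/0.1149 = 0.259. Times 0.748 at 12 months gives 0.194; times 0.936 at 24 months gives 0.242.

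| 6-month progression | Month | Life table | Cumulative incidence | Gap (points) |
|---|---|---|---|---|
| 25% | 12 | 30% | 23% | 7 |
| 25% | 24 | 51% | 32% | 19 |
| 40% | 12 | 30% | 19% | 11 |
| 40% | 24 | 51% | 24% | 27 |

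**Early times.** Here I let the assumed net toxicity be 10% to 30% at 6 months and use both progression rates. The gap is about 0.3 points or less at 1 month, 0.3 to 1.9 points at 3 months, 1.3 to 6.2 points at 6 months, and 13 to 36 points at 26 cycles.

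**Front-loaded toxicity.** I simulated 37 patients per arm (2,000 runs) with a Weibull toxicity time of shape 0.5 and 20% net toxicity at 6 months. At 26 cycles the life table and cumulative incidence average 36.4% and 27.2% with 25% progression, and 36.0% and 22.7% with 40%: gaps of 9 and 13 points. Constant hazards with the same 6-month toxicity give 58.9% against 38.0% and 58.9% against 28.8%: gaps of 21 and 30 points.

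**Progression from the EFS assumption.** Section 9.4 uses long-term EFS of 30% and 45% without a horizon. If these are taken as 24-month values (an assumption), hP = −ln(0.30)/24 = 0.0502 or −ln(0.45)/24 = 0.0333. With hT = 0.0297 the pairs become 30% against 23% to 25% at 12 months and 51% against 32% to 37% at 24 months.

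**The case against.** Several points on the other side stand.

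- **Scope.** Section 9.8 ties the time scale to acute and subacute toxicity, and the censoring sentence follows directly. There the gap is small. A reader might infer that the plan's answer to objective 1.2.4, toxicities of long-term use, will be overstated. The documents do not support that: long-term hematologic toxicity is handled per reporting period, and the per-course rates and the counts do not use the curve.
- **Dose comparison.** A reader might also infer that the toxicity comparison between doses is distorted. The only one stated is the per-period hematologic comparison; none is stated for the life table. Moreover, if both arms had hT = 0.0297 but 25% and 40% 6-month progression, both life tables would read 51% at 24 months while the cumulative incidences were 32% and 24%. The faster-progressing arm would look less toxic on cumulative incidence. For toxicity while on drug, the censored (cause-specific) analysis is a standard choice.
- **Target.** If progression is independent of toxicity, the censored curve validly estimates risk under continued treatment. But Section 9.8 does not say that this is the target, and independence is not assured: Section 2.4 describes a phase I patient with dose-limiting fatigue and concurrent progression.
- **Later toxicity.** Progression does not rule out toxicity. Patients are followed off therapy (Section 8.1), and attributable serious events more than 30 days after the last dose are reportable (Section 11.3.1). Censoring drops these, which acts in the opposite direction, so the point is confined to on-treatment toxicity.

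The scope argument does not dispose of the point, because neither subacute nor primary toxicity is defined and the curve has no stated end.

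**Conclusion.** The point holds in a limited form. One minus the progression-censored life table is never below the cumulative incidence of on-treatment toxicity, so it is too high if read as the proportion of treated patients affected. That direction does not depend on the assumed rates.

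The size does. It rests on a toxicity rate that the documents do not supply, on the hazard shape, and on extending the 6-month progression rates. The largest illustrated pair, 51% against 24%, uses the rate the plan calls inadequate; held constant, that rate leaves 0.60⁴ = 13% progression-free at 24 months, well below the 30% to 45% long-term EFS in Section 9.4. The 25% rate and the EFS-based rates give smaller late gaps.

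This concerns one secondary safety summary. The primary endpoint, the sample size and the stopping rules are untouched. The life table is not an invalid method; what is missing is a stated target and an estimate of the proportion affected.

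**What to change.** In Section 9.8:

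1. Define primary toxicity, the time horizon and the quantity to be estimated.
2. Report by regimen the cumulative incidence of first on-treatment toxicity (Aalen-Johansen), with progression, death and removal from therapy for other reasons as competing events. This also settles how death and other withdrawals are handled.
3. Keep the progression-censored estimate, labelled as toxicity risk under continued treatment (cause-specific), for comparing the doses while on drug.

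The change needs SAP wording and a standard routine, with no new data or patients. The cost is two toxicity summaries to explain. The cumulative incidence itself depends on how fast each arm progresses, so it should be shown beside the progression results and not used alone to judge which dose is more toxic.

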9.9 Analysis of Lenalidomide Pharmacokinetic Parameters

Correlation of lenalidomide concentration obtained from the steady-state sample and the number of cycles received prior to the occurrence of disease progression will be performed using Pearson's correlation coefficient. Cox regression analysis will be used to assess the association between outcome and steady state levels at a particular cycle.

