2.5 Rationale for Pharmacokinetic Studies

In order to obtain more information regarding a potential dose-response relationship and to further determine if myelosuppression is dose-related, pharmacokinetic studies will be performed in all patients in this study. Steady state PK levels of lenalidomide will be performed prior to administering the daily dose any day between Days 5-21 on Cycle 1 and again between Days 5-21 on any cycle following a dose reduction. Correlation of steady state levels and best response at the patient dose will be performed. A single blood sample (2 ml in a heparinized tube) will be collected at up to three time-points and pharmacokinetic analyses will be performed using HPLC.

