9.3.1.2 Secondary Endpoints

- Time to treatment failure (Event-free survival, EFS) – the time from study enrollment to tumor progression, tumor recurrence, death from any cause, or occurrence of a second malignant neoplasm.

- Time to death (Overall survival, OS) – the time from study enrollment to death from any cause.

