9.11 Effect of the Stratification on Response Rate

At enrollment, the number of prior therapies, classified as 2 or fewer versus more than 2 will be required to complete the treatment assignment process. The efficacy rule described in [Section 9.5](#) will be executed as written regardless of the number of prior therapies that a patient has received. The risk for EFS-event and death associated with receiving more than 2 prior regimens will be assessed using the stratified 1-sided log-rank test, with randomized regimen as the stratification factor. Only patients enrolled after approval of the proposed amendment will be considered in the analysis. If the resulting p-value is not significant at the 0.10 level or less, the EFS and OS results will be presented without regard to stratification factor.

The following logistic regression model will be utilized:

$$\Pr(CR \text{ or } PR | \underline{x}_i) = \frac{e^{x_i \beta}}{1 + e^{x_i \beta}};$$

where: x_{i1} is 1

x_{i2} is the random treatment assignment

x_{i3} is 1 if the patient received three or more prior regimens and 0 otherwise

The value and p-value associated with the estimate of β_3 will be used to infer whether there is evidence of an association between response rate and number of prior regimens

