13.0 SPECIAL STUDIES SPECIMEN REQUIREMENTS

13.1 Steady State Pharmacokinetic Study

Participation in the pharmacokinetic study is required. Peripheral blood will be collected from all patients, for correlation of steady state pharmacokinetic levels of lenalidomide with best response and EFS at the patient dose.

Serum samples will be assayed for lenalidomide by a validated high performance liquid chromatography assay with MS detection that has been developed for the quantitative determination of lenalidomide in biological matrices³⁰.

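### Section 9.9 applies Pearson's coefficient to a right-censored cycle count with no rule for patients who stop without progression; a pooled Cox model of EFS should be the PK–EFS analysis

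*Combined protocol and SAP*

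**What the plan says.** Objective 1.2.3 is "To correlate steady state pharmacokinetics of lenalidomide (1 sample obtained between Days 5-21) with objective response and EFS". Section 2.5 gives the purpose as learning about a possible dose-response relationship and promises that "Correlation of steady state levels and best response at the patient dose will be performed". Section 13.1 collects blood "for correlation of steady state pharmacokinetic levels of lenalidomide with best response and EFS at the patient dose".

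Section 9.9 offers two analyses. The first relates concentration to cycle count: "the number of cycles received prior to the occurrence of disease progression will be performed using Pearson's correlation coefficient". The second reads "Cox regression analysis will be used to assess the association between outcome and steady state levels at a particular cycle". It does not define the outcome or the cycle, name a method for objective response, say which analysis answers the EFS half of the objective, or mention regimen.

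Elsewhere:
- Section 9.3.1.2 defines EFS as "the time from study enrollment to tumor progression, tumor recurrence, death from any cause, or occurrence of a second malignant neoplasm". Section 9.4 assigns standard survival methods to it.
- Section 8.1 ends therapy at 26 cycles, and also for toxicity after two reductions, refusal, physician decision and other reasons that are not progression.
- Section 13.1.1 samples every patient before a dose on one of Days 5–21 of cycle 1. Later samples are taken only after a dose reduction.

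**The concern.** For a patient who stops without progression, the number of cycles before progression is known only to exceed the number received. Pearson's coefficient has no place for such a value. The analyst must drop these patients, enter them at their stopping cycle as if that were progression, or enter them at 26. Section 9.9 does not choose.

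Three things are at stake. The coefficient depends on an unstated choice. It carries less information than the survival model in the next sentence of the same section. And if patients with high exposure stop earlier for reasons other than progression, their shorter counts pull the coefficient towards a negative relation even where exposure helps. The Pearson and Cox results could also disagree, with nothing to say which one counts.

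**Working it through.** **1. The plan's own figure.** Section 9.4 states about 69% power for EFS of 30% vs 45%, 37 per arm, one-sided 20%. As two proportions: SE under the null = √(2 × 0.375 × 0.625/37) = 0.1126; SE under the alternative = √((0.30 × 0.70 + 0.45 × 0.55)/37) = 0.1112; power = Φ((0.15 − 0.842 × 0.1126)/0.1112) = 69.0%. The Freedman log-rank formula, with HR = ln 0.45/ln 0.30 = 0.663 and 37 × 0.70 + 37 × 0.55 = 46.25 events, gives 70.4%. The figure reproduces, so the same effect is used below.

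**2. How many counts are censored.**
- Planning EFS rates (9.4): 74 × 0.30 = 22; 74 × 0.45 = 33; one arm at each rate, 37 × 0.30 + 37 × 0.45 = 28.
- Six-month progression rates (9.5), assuming constant hazard to 26 × 28 = 728 days, or 3.99 half-years: 0.60^3.99 = 0.13 and 0.75^3.99 = 0.32, i.e. about 10 to 24 of 74.

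Neither range counts patients who stop early for other reasons.

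**3. The exposure effect implied by the plan.** The dose ratio is 115/20 = 5.75 and ln 5.75 = 1.749. If concentration is proportional to dose, the slope is ln 0.663/1.749 = −0.235 per log unit (HR 0.79). Between-arm variance of log concentration is 1.749²/4 = 0.765. Within-arm log SD is not in the documents; 0.5 is assumed first.

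**4. Cox power in closed form.** Power = Φ(0.235 × √(46.25 × variance) − 1.96), two-sided 5% (assumed; 9.9 states no level).

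| Model | Within-arm log SD | Variance used | Closed form | Simulation |
|---|---|---|---|---|
| Pooled | 0.5 | 0.765 + 0.25 = 1.015 | 36% | 38% |
| Stratified by regimen | 0.5 | 0.25 | 12% | 13% |
| Stratified by regimen | 1.1 | 1.21 | 42% | 40% |

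**5. Pearson against Cox, simulated.** 37 per arm, 3,000 or more trials per setting, log SD 0.5, baseline hazard −ln 0.30/26 per cycle, cycle count capped at 26. With 10% in each arm stopping without progression, power is 24% for Pearson in all patients, 7% for Pearson in progressors only, and 38% for pooled Cox. If Cox is censored at stopping, it is 35%.

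Unequal stopping (low/high dose, assumed), with a true benefit; ranges are over independent runs:

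| Stopping without progression | Mean r | Pearson wrong sign | Pooled Cox wrong sign |
|---|---|---|---|
| 10/10% | 0.14–0.15 | 11–12% | 5–6% |
| 10/20% | 0.08–0.09 | 22–25% | 5–6% |
| 10/30% | 0.01–0.04 | 38–45% | 5–6% |

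With no exposure effect, Pearson rejects in 4–6% of trials at 10/10 and 6% at 10/20. At 10/30 it rejects in 12–13%, nearly always in the negative direction. Cox stays near 5%.

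**6. The handling rule alone.** At the plan's slope, with no early stopping and a within-arm CV of 50%, mean r is 0.06 if non-progressors are dropped and 0.15 if they are entered at 26 cycles.

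**The case against.** The strongest reply is that a suitable method is already there: Section 9.9 names Cox regression and Section 9.4 assigns survival methods to EFS. That stands, and it is why the repair is only wording. It does not say what the Pearson result means or which result counts.

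Several stronger readings are tempting, and the documents do not support them.
- **That Pearson would show harm where there is benefit.** Mean r stays positive in every benefit scenario above, and a significant negative r occurred in about 1% of trials or fewer. What is lost is signal. The large distortion needs a 10% vs 30% stopping split. Section 2.4 reports only a possible trend to more myelosuppression at higher doses and calls it not clearly dose-related; Section 5.0 allows two dose reductions first.
- **That a pooled result mostly repeats the arm comparison.** At log SD 0.5 the arm explains 0.765/1.015 = 75% of variance. But the sample is a trough about 24 h after a once-daily dose, with a half-life near 3 h (6.1). A 20% CV in elimination rate (assumed) alone gives log SD 24 × (ln 2/3) × 0.20 = 1.1, and the share falls to 0.765/1.975 = 39%. The documented linearity is for peak and AUC, not trough.
- **That the main model should be stratified because Section 9.11 does so.** There, regimen is a nuisance factor in testing prior therapy: "stratified 1-sided log-rank test, with randomized regimen as the stratification factor". Here, the assigned dose is the randomised cause of exposure, and stratifying removes the contrast that Section 2.5 is after. At log SD 0.5 the stratified Cox model has the wrong sign in about 20% of trials, which is worse than Pearson at 10/10.
- **That five-year follow-up gives Cox complete progression data.** Sections 8.1 and 8.2 require follow-up data, but scheduled MRI ends at removal from therapy (7.1, 14.1). The 38% assumes full ascertainment; the 35% with censoring at stopping shows that most of the advantage does not depend on it.
- **That 22–33 is a patient count.** It is a planning EFS range, and EFS events include death and second malignancy.

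**Conclusion.** The point holds in limited form. Section 9.9 applies Pearson's coefficient to a right-censored count with no rule for patients without progression, perhaps 10–33 of 74 before other drop-out. The cost is lost power (24% against 38% in the illustration), a coefficient that depends on an unstated choice, and a bias towards a negative relation if non-progression stopping rises with exposure. Inflated false positives appear only in the most unequal scenario.

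The percentages rest on the plan's 30% vs 45% EFS effect, concentration proportional to dose, an assumed within-arm log SD of 0.5 and assumed stopping rates. The direction of the power comparison at equal stopping does not depend on the last: both closed form and simulation favour the pooled Cox model. Within-arm trough variability is unknown, so the power of a regimen-stratified model could be about 13% or about 40%.

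No stopping rule, sample size or primary analysis uses this result. It is a secondary, correlative objective.

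**What to change.** In Section 9.9:
1. Drop the Pearson analysis, or label it descriptive and state how patients without progression are entered.
2. Name as the PK–EFS analysis a pooled Cox model of EFS (9.3.1.2) on log cycle-1 concentration. Start time at the sample (landmark), and censor patients without an event at their last disease assessment. Use levels drawn after a dose reduction only as a time-dependent covariate.
3. Report a Cox model stratified by randomised regimen as a sensitivity analysis of exposure beyond assigned dose. Note that its power depends on within-arm trough variability. Do not state in advance that the pooled result largely reflects the arm comparison.
4. For the response half of objective 1.2.3, add logistic regression of CR/PR on log cycle-1 concentration.

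Optionally, record the date and time of the previous dose on Appendix VII, which now asks only for the dose given after the sample. At a 3 h half-life, a 2 h error in that time changes a trough 2^(2/3) = 1.6-fold; the real size of such errors is unknown.

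The cost is analysis-plan wording and, if wanted, one field on an existing form. No extra patient, visit or sample is needed.
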